6.3.9 Follow-up Visits for Early Termination from Post-Treatment Follow-up Period

The patient who requests to withdraw from the study during the Post-Treatment Follow-up Period should be encouraged to have a home nurse visit for safety/efficacy labs (equivalent to week 74 visit in Appendix A) and telephone follow-up, ideally ~12 weeks from the last dose of Study Drug.

If a patient withdraws due to an AE at any time during the study, the Investigator will arrange for the patient to have appropriate follow-up until the AE has resolved or stabilized. Appropriate follow up may include home nursing visits or visits to NIH if necessary.

6.3.10 End of Study

After completion of this study, subjects may continue to receive care through NIH via protocol 76-DK-0006 (Studies of Molecular Genetics of Insulin Secretion, Insulin Action and Diabetes Mellitus), but cannot continue to take the study drug through this study.

6.3.11 Post-Study Obligations

There are no anticipated post-study obligations.

6.4 Study Assessments

6.4.1 Patient Reported Outcomes

1. **Hunger and Widespread Pain Diaries:** All patients will complete hunger and pain questionnaires at each in-person visit. (Appendix H).
2. **Quality of Life Assessments:** All patients will complete Quality of Life Questionnaires (EQ-5D and SF-36) at each in-person visit. (Appendix F & G).

6.4.2 Detailed Metabolic Phenotyping

1. **Anthropometric measurements:** Physical exams and vital signs will be performed as indicated in the Schedule of Procedures (Appendix A). Height will be measured in the early morning on the first full day of the first inpatient visit. Vital signs will include weight, blood pressure, pulse rate, respiratory rate and body temperature. Blood pressure and pulse rate will be recorded after the patient has been in a sitting position for at least 5 minutes. Systolic and diastolic blood pressure should always be measured on the same arm (preferentially on the left arm). Waist circumference will be measured at the iliac crest in triplicate to the nearest tenth of a cm using a stretch-less, tension-sensitive tape measure at the times indicated in the Schedule of Procedures (Appendix A). Skinfold measurements will be obtained in triplicate to the nearest mm using regularly calibrated Lange skinfold calipers at the times indicated in the Schedule of Procedures (Appendix A).

2. Fasting labs: Blood samples will be obtained following a minimum 8 hour fast for analytes described in Appendix A. Ideally the morning blood draw will be coordinated so that it will be collected 10 hours after the evening meal. Additional serum and plasma samples will be stored for future analysis.
3. DEXA scan for total body composition: DEXA scans will be conducted prior to administration of the first dose of study drug and repeated after the 16 week placebo controlled period, and again after 16 weeks of open-label drug in those previously assigned to placebo. A DEXA scan (iDXA, GE Healthcare, Madison WI) will be performed to determine total and regional body fat and lean soft tissue masses, bone mineral content and density. DEXA produces photons at two different energy levels, 40 and 70 KeV. The photons pass through tissues and attenuate at rates related to elemental composition. Bone mineral, with highly attenuating calcium and phosphorous, is readily distinguished from soft tissues. The different elemental profiles of fat and bone-mineral free lean components allows for the analysis of soft tissue fat content, so that bone mineral, fat, and bone mineral fat-free lean components may be resolved.
4. Glucose and Lipid Turnover: Stable isotope tracers will be used to measure glucose and lipid turnover. Endogenous glucose production will be measured using steady-state infusion of [6,6- $^2\text{H}_2$]glucose tracer. The fractional rate of gluconeogenesis will be measured using steady-state oral dosing of deuterated water ($^2\text{H}_2\text{O}$) ⁴⁵. The rate of lipolysis will be measured using steady-state infusion of deuterium-labeled $^2\text{H}_5$ -glycerol, and the fatty acid turnover rate will be measured using steady-state infusion of [U- $^{13}\text{C}_{16}$] palmitate. Subjects will fast after 8 pm. A total of 3 grams per kg lean body mass of $^2\text{H}_2\text{O}$ will be given in four divided doses every two hours at 9 pm, 11 pm, 1 am, and 3 am in order to enrich the subject's body water pool to approximately 0.5% $^2\text{H}_2\text{O}$. Beginning at ~5 am, a primed [6,6- $^2\text{H}_2$]glucose infusion will be given for 3 hours, after which blood samples to measure isotope enrichment will be measured over a period of 30 minutes at steady state. Two hours after the [6,6- $^2\text{H}_2$]glucose infusion begins, a primed $^2\text{H}_5$ -glycerol infusion, and unprimed [U- $^{13}\text{C}_{16}$] palmitate infusion will be given for one hour, and isotope enrichment will be measured over a period of 30 minutes at steady state. To assess the effects of hyperinsulinemia on glucose turnover, the glucose tracer infusion will be continued during the euglycemic, hyperinsulinemic clamp study, below, with blood samples for tracer enrichment obtained during the steady-state period of the clamp.
5. Euglycemic Hyperinsulinemic Clamp: This is the gold-standard test to measure insulin sensitivity. For insulin treated subjects, an overnight insulin drip may be given beginning at 6 pm the night prior to the clamp to maintain euglycemia. After an 8-hour fast, insulin will be infused at a dose of 120 mcU/m²*minute. This dose is designed to suppress endogenous glucose production and near-maximally stimulate glucose uptake in this group of very insulin resistant subjects. 20% dextrose enriched with 2.5% [6,6- $^2\text{H}_2$]glucose tracer will be infused at a variable rate to maintain blood glucose at approximately 100 mg/dL. If subjects remain hyperglycemic without dextrose infusion after 1 hour of insulin infusion (by which time maximum insulin effect is expected), a higher steady state blood glucose concentration for the clamp may be used. During the insulin infusion, blood samples (0.5 mL) will be obtained every 5 minutes to measure blood glucose at the bedside. At steady state, the rate of dextrose infusion provides an estimate of insulin-stimulated glucose disposal. Additional samples will be drawn to measure the glucose and lipid tracers (described above), insulin,

and other hormone levels. If technical problems occur with a clamp study (e.g. IV failure or failure to attain steady-state glucose and insulin levels), the clamp may be repeated if blood volume limits permit.

6. Mixed meal test: The effect of a standardized liquid meal (Boost-plus) with fixed, balanced macronutrient content will be assessed. Blood samples will be obtained for glucose, insulin, C-peptide, lipid analysis, and research storage at -10, 0, 30, 60, 120, 180, 240, 300 and 360 minutes after consuming the liquid meal. Visual analog scales for hunger and satiety will be obtained at the 0 and 60 minute time points.
7. Lipoprotein lipase activity: Measurement of lipoprotein lipase and hepatic lipase activities in plasma will be performed using blood samples obtained 10 minutes after intravenous infusion of 60 units/kg of unfractionated heparin using the methods of Iverius and Nilsson-Ehle^{46,47}. Lipoprotein lipase and hepatic lipase are bound to vessel walls and only released into the blood with an infusion of heparin.
8. Magnetic Resonance Imaging (MRI) and Magnetic Resonance Spectroscopy (MRS): Hepatic, muscle and central body fat will be measured by magnetic resonance imaging (MRI) and magnetic resonance spectroscopy (MRS). Studies are performed on a 3T MRI scanner using phased-array coils. Hepatic and muscle fat fraction will be determined⁴⁸. Visceral and subcutaneous fat measurements will be obtained using standard T1 Spin Echo technique which presents fat as a bright signal that can be segmented for area and volume measurements. In addition, MRI scanning will be performed for angiography (without gadolinium), vessel wall, and endothelial function⁴⁹. Each subject will be asked to perform a hand-grip exercise to obtain arterial dimensions. Before entering the magnet, we shall measure the maximal force production while hand squeezing a nonmagnetic hand-grip device. Later in the magnet at roughly one quarter of his/her maximal force, we will obtain MR data before, during, and after this exercise. The use of the device will be continuously monitored and the subject will be able to switch hands if one hand becomes fatigued.
9. Carotid intima-media thickness (cIMT): cIMT is an established marker of coronary artery disease and cardiovascular risk. This is a non-invasive test using ultrasonography of the carotid arteries in the neck.
10. 7-point plasma glucose: Plasma glucose will be measured prior to each meal, 90 minutes after each meal, and at bedtime. Area under the curve for glucose will be calculated using the trapezoidal method.
11. Liver biopsy: An optional liver biopsy will be performed in patients at the initial visit and at the end of the open label extension period (after 12-16 months of exposure to ISIS 304801). Biopsies will be performed transcutaneously unless there is a clinical reason for another approach (e.g. transjugular). These biopsies are performed primarily for research purposes, although clinical data about the severity of non-alcoholic fatty liver disease (NAFLD) or non-alcoholic steatohepatitis (NASH) will be obtained as well. Patients will sign a research consent for each liver biopsy prior to the procedure. Patients will be allowed to refuse the biopsies and continue to participate in the rest of the study. Platelet count will be obtained prior to percutaneous liver biopsy, and the biopsy will not be

performed if patients have evidence of coagulopathy unresponsive to vitamin K (INR >1.5) or low platelets (Platelets < 75,000 k/uL) which may place them at a potentially higher risk for bleeding. About half of the liver biopsy sample will be fresh frozen in liquid nitrogen and will be stored for molecular analyses and Metabolomics studies in collaboration with [name] at the University of Michigan.

Histologic analysis: Specimens will be graded for the severity of NAFLD/NASH pathology. Histological features of NAFLD/NASH will be studied using the validated NASH-CRN (NASH Clinical Research Network) scoring system (3). This scoring system comprises histological features, 4 of which [steatosis (0-3), lobular inflammation (0-3), hepatocellular ballooning (0-2) and fibrosis (0-3 with grade 1 divided in three categories as well)] are evaluated semi-quantitatively. NAFLD activity score (NAS) is the unweighted sum of steatosis, lobular inflammation and hepatocellular ballooning scores. Total of this together with the fibrosis score constitutes the total NASH score.

12. **Metabolomics:** Studies will be done in the Molecular Phenotyping Core of the Michigan Metabolomics and Obesity Center at the University of Michigan in collaboration with [name]. Plasma samples collected in the fasting state and liver biopsy samples will be extracted according to the method of Bligh and Dyer ⁵⁰ for analysis. Lipomic studies will include measurement of subclasses of lipids and fatty acid composition. Unbiased metabolomics studies of plasma will be conducted using LC/MS and GC/MS.

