3.2 Exclusion Criteria

1. A diagnosis of generalized lipodystrophy
2. Current or history of autoimmune diseases (even with a diagnosis of PL) unless approved by the Investigator and Sponsor Medical Monitor
3. Acute pancreatitis within 4 weeks of enrollment
4. History within 6 months of enrollment of acute or unstable cardiac ischemia (myocardial infarction, acute coronary syndrome, new onset angina), stroke, transient ischemic attack, or unstable congestive heart failure requiring a change in medication
5. Major surgery within 3 months of enrollment
6. History of heart failure with New York Heart Association functional classification (NYHA) greater than Class II
7. Uncontrolled hypertension (blood pressure [BP] >160/100 mm Hg)
8. Any of the following laboratory values at enrollment:
 - a. Cardiac troponin T >ULN
 - b. Measured or estimated (in case of triglycerides > 400 mg/dL) LDL-C >130 mg/dL on maximal tolerated statin therapy
 - c. Hemoglobin HbA1c ≥9.5%
 - d. Hepatic:
 - i. Total bilirubin >ULN
 - ii. ALT >3.0 x ULN. Higher levels will be permitted after a safety review by a hepatologist, that includes no evidence of cirrhosis.
 - iii. AST >3.0 x ULN. Higher levels will be permitted after a safety review by a hepatologist, that includes no evidence of cirrhosis.
 - e. Renal:

[figure not shown]
- i. Persistently positive (2 out of 3 tests \geq trace positive) for blood on urine dipstick. In the event of a positive test eligibility may be confirmed with urine microscopy showing \leq 5 red blood cells per high power field (urine will be screened at admission and repeated if abnormal). If RBC are high every effort will be made to determine if the source is renal or benign, such as from menstrual bleeding. If the presence of RBC is determined to be from a non-renal source, the PI will make the decision to proceed with protocol testing and/or randomization.
 - ii. Two out of three consecutive tests \geq 1+ for protein on urine dipstick. In the event of a positive test eligibility may be confirmed by either a spot urine albumin to creatinine ratio $<$ 1000mg/g or a quantitative total urine albumin measurement of $<$ 1g/24 hrs (urine will be screened at admission and repeated if abnormal)
 - iii. Estimated creatinine clearance calculated according to the formula of Cockcroft and Gault $<$ 60 mL/min
 - f. Platelet count below 140,000 K/uL

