4.2 Outcome Measures

4.2.1 Primary outcome:

Efficacy of 16 weeks of ISIS 304801 as compared to placebo (between group comparison) on the change in log₁₀ fasting triglycerides (TG).

4.2.2 Secondary outcomes:

Efficacy of 16 weeks of ISIS 304801 as compared to placebo (between group comparison) on:

Lipids

- Percent change in fasting TG
- Absolute change in fasting TG
- Change in lipolysis rate measured using stable isotope tracers
- Change from baseline in liver volume and hepatic steatosis (as assessed by magnetic resonance imaging [MRI] and magnetic resonance spectroscopy [MRS])
- Lipoprotein lipase activity

Glycemic

- Change in total body insulin sensitivity using the hyperinsulinemic euglycemic clamp
- Change in hepatic glucose production and hepatic insulin sensitivity using stable isotope tracers in combination with the hyperinsulinemic euglycemic clamp
- Change in hemoglobin A1c (HbA1c)
- Change in fasting plasma glucose

Safety

- Safety and tolerability of ISIS 304801
- Prospectively adjudicated acute pancreatitis events (Atlanta classification) and Major Adverse Cardiovascular Events (MACE)

Pharmacokinetic

- Plasma ISIS 304801 level

4.2.3 Tertiary/Exploratory outcomes:

Efficacy of 16 weeks and 16 months of ISIS 304801 as compared to immediately prior to treatment (pre-post within subject comparison) on:

Lipids

- Change in other fasting lipid measurements: high-density lipoprotein cholesterol (HDL-C), low-density lipoprotein cholesterol (LDL-C), total cholesterol (TChol), very low-density lipoprotein cholesterol VLDL-C, non-HDL-C, apolipoprotein B (apoB), apolipoprotein B-48 (apoB48), apolipoprotein A1 (apoA1), apolipoprotein CIII (apoC-III; total, chylomicron, VLDL, LDL and HDL), and free fatty acids
- Change in lipoprotein particle size/number by nuclear magnetic resonance (NMR)
- Triglyceride (and other lipid particle) clearance following mixed meal testing

Glycemic

- Change in 24-h glucose (using 7-point plasma blood glucose)
- Change in fasting and area under the curve for insulin and C-peptide during mixed meal testing
- Reduction in insulin use

Adipose tissue

- Change in skinfold thickness and dual-energy X-ray absorptiometry (DEXA)
- Change in abdominal VAT and SAT volumes
- Change in adiponectin and leptin
- Change in body weight and waist circumference

Cardiovascular

- Carotid intima-media thickness (by ultrasound)
- Coronary artery wall thickness and diameter change after hand-grip exercise (by MRI)

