	Absolute change serum triglycerides (mg/dL)	High TG +/- diabetes and/or fibrate	ApoCIII ASO 300 mg/wk	16 wk	-423 (400)	0.85
Secondary outcomes	Hemoglobin A1C (%)	Type 2 diabetes	ApoCIII ASO 300 mg/wk	16 wk	-0.2 (0.36)	0.35
	Total body insulin sensitivity (glucose infusion rate during clamp, mg*kg ⁻¹ *min ⁻¹)	Type 2 diabetes	ApoCIII ASO 300 mg/wk	16 wk	1.6 (1.2)	>0.95
	Hepatic insulin sensitivity (% suppression of endogenous glucose production during clamp)	Type 2 diabetes	ApoCIII ASO 300 mg/wk	16 wk	11.0 (5.6)	>0.95
	Fasting plasma glucose (mg/dL)	Type 2 diabetes	ApoCIII ASO 300 mg/wk	16 wk	-35 (36)	0.78

	ApoCIII serum level (mg/dL)	High TG +/- diabetes and/or fibrate	ApoCIII ASO 300 mg/wk	16 wk	-15.3 (7.5)	>0.95
	HDL-C (mg/dL)	High TG +/- diabetes and/or fibrate	ApoCIII ASO 300 mg/wk	16 wk	13.3 (10.1)	>0.95
Tertiary Outcomes	LDL-C (mg/dL)	High TG +/- diabetes and/or fibrate	ApoCIII ASO 300 mg/wk	16 wk	31.3 (47.3)	0.46
	Total Cholesterol (mg/dL)	High TG +/- diabetes and/or fibrate	ApoCIII ASO 300 mg/wk	16 wk	-32 (72)	0.24
	VLDL-C (mg/dL)	High TG +/- diabetes and/or fibrate	ApoCIII ASO 300 mg/wk	16 wk	-77 (60)	0.95
	non-HDL-C (mg/dL)	High TG +/- diabetes and/or fibrate	ApoCIII ASO 300 mg/wk	16 wk	-46 (74)	0.42
	Apolipoprotein B (mg/dL)	High TG +/- diabetes and/or fibrate	ApoCIII ASO 300 mg/wk	16 wk	-5.8 (30)	0.09
	Apolipoprotein B-48 (mg/dL)	High TG +/- diabetes and/or fibrate	ApoCIII ASO 300 mg/wk	16 wk	-0.44 (0.43)	0.82
	Free Fatty Acids (uEq/L)	Familial chylomicron-emia	ApoCIII ASO 300 mg/wk	16 wk	-0.40 (0.44)	0.73
	Body Weight (kg)	High TG +/- diabetes and/or fibrate	ApoCIII ASO 300 mg/wk	16 wk	-0.87 (1.69)	0.30

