7. Glucose and Lipid Turnover: The stable isotopes ¹³C is not associated with any toxicity at the doses used in these studies ⁵⁴. Deuterium at the doses given may cause temporary dizziness. This risk will be minimized by dividing the ²H₂O dose into four aliquots, and by giving the doses at night while subjects lie in bed. If subjects need to get out of bed (e.g. to use the bathroom) the patient will first sit upright in bed for a few minutes prior to standing, and a nurse will be available to supervise and assist. Palmitate must be complexed to albumin prior to delivery, and thus carries the risks associated with use of human blood products. To minimize exposure to human albumin, uniformly labeled ¹³C₁₆ palmitate will be used, permitting use of the minimum possible dose of this tracer.
8. Euglycemic Hyperinsulinemic Clamp Study: In order to assess insulin sensitivity, patients will receive an intravenous infusion of insulin and – via a second intravenous access – increasing amounts of glucose to maintain euglycemia. Insertion of the necessary intravenous lines may cause the above-mentioned discomfort and a possible skin infection. Insulin infusion can induce hypoglycemia and hypokalemia. Either event is very unlikely, since patients undergo frequent blood glucose measurements and are constantly observed for the presence of hypoglycemic symptoms by an experienced nurse and/or physician. However, in order to prevent complications, two patent, well-functioning intravenous lines are required during this procedure. A stat potassium will be measured at the end of the insulin infusion, and oral KCL 40 mEq will be given if potassium is less than 3.5.

9. Magnetic Resonance Imaging (MRI) and Magnetic Resonance Spectroscopy (MRS): While MR scanning is thought to be safe, the procedure may cause anxiety in some patients since current equipment used at the Clinical Center uses a closed tube. Adult patients will be offered sedatives such as Valium if they express worry about being in a closed space. No intravenous contrast will be used in these studies. The hand-grip exercise may produce mild fatigue.

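### The clamp insulin rate is printed in micro-units (about 0.013 U/h), too little for its stated purpose; the intended unit was probably mU, a thousand times larger

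*Combined protocol and SAP*

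**What the plan says.** The clamp is described in section 6.4.2, item 5. After the fast, "insulin will be infused at a dose of 120 mcU/m²*minute". The purpose follows at once: "This dose is designed to suppress endogenous glucose production and near-maximally stimulate glucose uptake in this group of very insulin resistant subjects". Labelled dextrose is then infused at a variable rate to hold glucose near 100 mg/dL. A patient who is still hyperglycemic without dextrose after one hour of insulin is treated as an exception and may be clamped at a higher glucose level.

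Other sections rely on this infusion:

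- Section 6.4.2, item 4, on the tracers: "To assess the effects of hyperinsulinemia on glucose turnover, the glucose tracer infusion will be continued during the euglycemic, hyperinsulinemic clamp study".
- Section 7.10.2, on the risks of the clamp: "Insulin infusion can induce hypoglycemia and hypokalemia".
- Section 4.2.2 lists as a secondary outcome "Change in total body insulin sensitivity using the hyperinsulinemic euglycemic clamp", and also lists hepatic insulin sensitivity by tracer combined with the clamp.
- The table in section 5.1 expresses hepatic insulin sensitivity as the percentage "suppression of endogenous glucose production during clamp".

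The insulin rate is not repeated in any of these places, so the line in item 5 stands alone.

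**The concern.** The prefix mc denotes micro. A rate of 120 micro-units per m² per minute is a negligible amount of insulin, yet the text around it describes a high-dose clamp in patients who respond poorly to insulin. The number with its unit and the purpose in the next sentence cannot both be right. The simplest explanation is a clerical slip of a factor of 1000, with mU intended.

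This line is the operative instruction for an intravenous study infusion. If it were followed as printed, insulin would hardly rise. The dextrose rate would not measure insulin-stimulated glucose disposal, and the fall in glucose production would not measure the liver's response to insulin. Two secondary outcomes that section 5.1 names as adequately powered would lose their meaning. Even if the staff used the correct rate, a reader of the public document cannot interpret or compare the clamp results without knowing what was infused.

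**Working it through.** **Inputs**

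- Rate as printed: 120 mcU/m²/min = 120 × 10⁻⁶ U/m²/min (section 6.4.2, item 5).
- Rate if mU was meant: 120 × 10⁻³ U/m²/min.
- Body surface area (BSA): not in the document. Assumed 1.8 m², range 1.5 to 2.5 m².
- Internal yardstick: section 3.1, minor criterion a, gives 200 U/day as one example of a high insulin requirement. 200 / 24 = 8.33 U/h.

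The plan gives no U/h equivalent and no derivation of the rate, so there is no figure of its own to reproduce.

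**Conversion**

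Rate in U/h = rate in U/m²/min × BSA × 60. At 1.8 m²:

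- As printed: 120 × 10⁻⁶ × 1.8 × 60 = 0.01296 U/h.
- As mU: 120 × 10⁻³ × 1.8 × 60 = 12.96 U/h.

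| BSA (m²) | As printed, mcU (U/h) | 8.33 U/h ÷ printed rate | If mU (U/h) | mU rate ÷ 8.33 U/h |
|---|---|---|---|---|
| 1.5 | 0.0108 | 772 | 10.8 | 1.30 |
| 1.8 | 0.0130 | 643 | 13.0 | 1.56 |
| 2.5 | 0.0180 | 463 | 18.0 | 2.16 |

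The printed rate is 460 to 770 times below the yardstick. The mU rate is 1.3 to 2.2 times above it. No plausible BSA closes a gap of that size, so the BSA assumption does not drive the conclusion.

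**Consistency with the rest of the text**

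| Statement in the protocol | 0.013 U/h | 13 U/h |
|---|---|---|
| Suppresses glucose production and nearly maximizes uptake (6.4.2, item 5) | No | Fits |
| Dextrose needed to hold glucose near 100 mg/dL; hyperglycemia without dextrose at one hour is the exception (6.4.2, item 5) | No | Fits |
| Produces hyperinsulinemia (6.4.2, item 4) | No | Fits |
| May cause low glucose and low potassium (7.10.2) | No | Fits |

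**Do the stated powers depend on the rate?**

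A one-sample t-test with n = 10 and two-sided 0.05, using the means and SDs in the section 5.1 table, gives:

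- Glucose infusion rate, 1.6 (SD 1.2): power 0.962; the table states >0.95.
- Suppression of glucose production, 11.0 (SD 5.6): power 0.9998; the table states >0.95.

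Both agree with the table, and neither uses the insulin rate. The primary comparison (5 per arm, difference 0.50, SD 0.25) gives 0.791 against the stated 79%, and it does not use the rate either.

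**The case against.** The strongest reply is that this is a typing error that would expose itself. The intended effect stands in the next sentence, and experienced staff would not set a pump to 0.013 U/h. Section 6.4.2 calls for bedside glucose every five minutes and for insulin samples during the clamp, and it allows a repeat if steady glucose and insulin levels are not reached. Section 7.10.2 adds constant observation and a potassium check. Basal glucose production is measured by tracer before the clamp and does not depend on this rate. The mention of five enrolled patients in section 7.14 suggests that the clamps may already be done, although it does not settle the matter.

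Most of this stands, and it limits the practical harm. It does not make the line correct. The insulin samples would show the failure only afterwards, and a repeat at the printed rate would fail in the same way.

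Two further cautions also stand. First, mU is an inference: the document contains no dose-response information, and the 200 U/day yardstick is one example within one optional criterion, so it does not describe every patient. Second, the platelet limits "Platelet count below 140,000 K/uL" (section 3.2) and "Platelets < 75,000 k/uL" (section 6.4.2, item 11) are also wrong by a factor of 1000, as section 7.6.3 shows by using 140K/mm³ and 75,000/mm³. Those errors make the value too large and come from a redundant multiplier. They show that units were not checked closely, but they say nothing about which insulin unit was meant.

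A fault in reading the PDF cannot be wholly excluded. It is unlikely: a stray inserted c is improbable, and a misread micro sign would still mean micro-units.

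**Conclusion.** The line is wrong as written, and that is certain: about 0.013 U/h (0.011 to 0.018 U/h for an assumed BSA of 1.5 to 2.5 m²) cannot produce the effect the protocol claims for it, and no other section corrects it. That mU was intended, giving about 13 U/h (10.8 to 18.0 U/h), is probable but unconfirmed. The consequence is confined to the insulin-stimulated secondary outcomes and to how the clamp results can be read. The primary outcome, sample size, power and analysis are untouched, and there is no evidence that a patient was clamped at the wrong rate. It should be fixed because it is an operative dosing figure and the correction is nearly free.

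**What to change.** - Check the source page and the clamp order set to establish the rate and unit actually used.
- Amend section 6.4.2, item 5, to that rate, presumably by replacing mcU with mU.
- State the delivered insulin rate wherever clamp results are reported.
- In the same amendment, remove the redundant K from the two platelet limits in sections 3.2 and 6.4.2.

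The cost is one check of the order set and a few characters in an amendment, with no change to design, sample size or analysis. If all clamps are complete, the correction still matters for the record and for the report.

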5.1 Sample Size Justification

The primary outcome variable is the change in log₁₀ fasting triglycerides from before treatment to 16 weeks of active drug treatment compared to placebo groups.

Preliminary data are available for 28 patients treated with ISIS 304801 and 24 treated with placebo. For the ISIS 304801 group, these data show a difference from baseline to follow-up of -423 (SD 400, 95% CI -578 to -268) mg/dL and -0.485 (SD 0.221, 95% CI -0.57 to -0.40) log₁₀ mg/dL. Converting the difference in log₁₀ mg/dL to a percent change [$100 \times (10^{-0.485} - 1)$] results in a percent change of -67% (95% CI -73% to -60%). For the placebo group, the absolute change is -12 (SD 406, 95% CI -12 to 184) mg/dL and -0.011 (SD 0.224, 95% CI -0.105 to 0.084) log₁₀ mg/dL. The percent change for the placebo group is -3% (95% CI -21% to 21%).

For comparison of placebo and ISIS 304801 we have chosen a SD of 0.25 log₁₀ mg/dL and a difference of 0.50 log₁₀ mg/dL. A trial with 5 patients in each group has 79% power to detect a difference of 0.50 log₁₀ mg/dL triglycerides in the change from baseline to follow-up between the ISIS and placebo groups, assuming a SD of 0.25 log₁₀ mg/dL and a two-sided significance level of 0.05.

Where preliminary data were available, sample size calculations were performed for secondary and tertiary study outcomes in addition to the primary outcome. The preliminary data and power estimates for a sample size of 10 subjects (using one-sample t-test for off versus on drug comparisons) are summarized in the table below. Based on these calculations, the study should be adequately powered to detect differences in total body insulin sensitivity, hepatic insulin sensitivity, fasting glucose, apoC-III serum level, HDL-C, VLDL-C, and apolipoprotein B48.

Based on these calculations, we plan to enroll a maximum of 20 patients, with a goal of 10 patients completing the study (defined as completing 16 weeks of active drug treatment). The accrual ceiling of 20 is planned because subjects will consent to the study prior to screening, thus we are accounting for up to 10 screen failures in the accrual ceiling.

	Outcome	Model	Treatment	Treat- ment Duration	Mean of Δ on-off drug (SD)	Power
Primary outcome	Absolute change log[serum triglycerides] (mg/dL)	High TG +/- diabetes and/or fibrate	ApoCIII ASO 300 mg/wk	16 wk	-0.48 (0.22)	>0.95
	% change serum triglycerides (%)	High TG +/- diabetes and/or fibrate	ApoCIII ASO 300 mg/wk	16 wk	-63 (20)	>0.95

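### The clamp glucose level may differ between visits, but insulin sensitivity is read as the raw glucose infusion rate with no allowance for the glucose achieved

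*Combined protocol and SAP*

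**What the plan says.** Section 6.4.2, item 5, describes the clamp. Tracer-enriched dextrose "will be infused at a variable rate to maintain blood glucose at approximately 100 mg/dL". An exception follows: "If subjects remain hyperglycemic without dextrose infusion after 1 hour of insulin infusion", then "a higher steady state blood glucose concentration for the clamp may be used". No value or ceiling is given for the higher level, and no rule ties later clamps to the level used at baseline. The read-out is stated this way: "At steady state, the rate of dextrose infusion provides an estimate of insulin-stimulated glucose disposal".

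Section 4.2.2 lists the secondary outcome as "Change in total body insulin sensitivity using the hyperinsulinemic euglycemic clamp", compared between drug and placebo, without a formula. The power table in section 5.1 names the measure, "Total body insulin sensitivity (glucose infusion rate during clamp", in mg/kg/min. The assumed mean change is 1.6 (SD 1.2), the model population is "Type 2 diabetes", and the stated power is above 0.95. The table gives "power estimates for a sample size of 10 subjects (using one-sample t-test for off versus on drug comparisons").

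Section 5.2 tests the change at Week 16 with a two-sample t-test or rank sum test. It names three candidate covariates for the mixed models: baseline outcome, baseline apoC-III and change in apoC-III. Clamp glucose is not among them.

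**The concern.** At a fixed insulin level, more glucose is cleared when blood glucose is higher. Infusion rates taken at different glucose levels therefore do not measure the same thing, either within a patient or between patients.

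The change of level would not be random. Its trigger is failure to come down under insulin, and improved insulin response is one of the trial's hypotheses. A patient who responds to the drug could be clamped high at baseline and near 100 mg/dL at Week 16. The lower glucose would then reduce the raw rate and hide part of the gain.

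The exception is not remote. Section 6.4.2 itself describes these subjects as highly insulin resistant. One entry route in section 3.1 requires HbA1c above 7%, and section 3.2 excludes only values of 9.5% or more. The overnight insulin drip is optional, is limited to insulin-treated patients and comes before the clamp, so it does not remove the problem.

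Section 5.1 counts total body insulin sensitivity among the outcomes for which the study is adequately powered.

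**Working it through.** **1. The plan's own figure.** One-sample t-test, n = 10, two-sided 0.05. That level is stated for the primary comparison and assumed here for the table. Standardised effect 1.6/1.2 = 1.333; noncentrality 1.333 × √10 = 4.22; exact power 0.962. The stated figure of above 0.95 reproduces. So do other rows, such as HbA1c (0.349 against 0.35) and fasting glucose (0.781 against 0.78).

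**2. The comparison that defines the secondary outcome.** With 5 per arm the noncentrality is 1.333 × √(5/2) = 2.11, and exact power is 0.458. The effect detectable with 80% power is 1.20 mg/kg/min pre-post (n = 10) and 2.43 between groups.

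**3. Shift in one patient, simple model.** Assume that disposal is proportional to glucose. Let M be disposal at 100 mg/dL (mg/kg/min) and G the higher level. The shift from moving between G and 100 is A = M × (G − 100)/100. The documents give neither M nor G, so a range is shown.

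| M | G = 140 | G = 180 | G = 200 | G at which A = 1.6 |
|---|---|---|---|---|
| 1 | 0.4 | 0.8 | 1.0 | 260 |
| 2 | 0.8 | 1.6 | 2.0 | 180 |
| 3 | 1.2 | 2.4 | 3.0 | 153 |
| 4 | 1.6 | 3.2 | 4.0 | 140 |

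**4. Shift in one patient, trigger taken at steady state.** Suppose the patient has truly levelled off at glucose P without dextrose, with residual glucose production E. Then disposal per unit glucose is k = E/P, and the shift is k × (G − 100).
- Lowest case: E = 0.5, P = 120, G = 140 gives (0.5/120) × 40 = 0.17.
- Highest case: E = 2, P = 200, G = 250 gives (2/200) × 150 = 1.5.

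Over E of 0.5 to 2, P of 120 to 200 and G set 20 to 50 above P, the range is 0.17 to 1.5, always below 1.6.

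**5. Can the larger values in step 3 be excluded?** No, because the trigger is read at 1 hour and not at a proven plateau. Assume M = 3, a starting glucose of 270 mg/dL (the early fasting alert level in section 7.5.8), a glucose space of 1.8 dL/kg, half the full insulin effect on average over the hour, and no residual production. Glucose at 60 minutes is then 270 × exp(−0.015 × 60/1.8) = 164 mg/dL. Such a patient meets the trigger without very low disposal.

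**6. Effect on a group mean.** If m of n patients switch, the mean moves by A × m/n. With A = 1.6, one of 5 moves it by 0.32, and all 5 must switch to move it by 1.6. With A = 2.4, one of 5 moves it by 0.48, and four are needed to reach 1.6 (2.4 × 4/5 = 1.92).

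**7. Effect on power.** Simulation with 100,000 trials per case, true effect 1.6, SD 1.2. Switched patients are high at baseline and at 100 mg/dL at Week 16. In the between-group case they are all in the active arm.

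| Shift per switched patient | Switched | Pre-post, n = 10 | Between groups, 5 per arm |
|---|---|---|---|
| none | 0 | 0.96 | 0.46 |
| 0.8 | 1 | 0.94 | 0.37 |
| 0.8 | 2 | 0.91 | 0.30 |
| 1.6 | 1 | 0.89 | 0.27 |
| 1.6 | 2 | 0.77 | 0.14 |

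**The case against.** A reader might infer that a change of level can outweigh the effect the trial is powered to detect, for example 2.4 mg/kg/min (M = 3, from 180 to 100 mg/dL) against 1.6. The documents do not support that, for four reasons.

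- **Patient against mean.** The 2.4 is one patient's shift under assumed values; 1.6 is a group mean. It is powered only in the pre-post test of 10 and was taken from type 2 diabetes.
- **The trigger selects low disposal.** At M = 3, a patient level at 150 mg/dL without dextrose would need glucose production of 3 × 1.5 = 4.5 mg/kg/min, under an insulin dose meant to suppress it. Patients who qualify should tend to be those with the smallest shift.
- **An unchanged patient would generally meet the trigger again.** An apparent loss of sensitivity with no true change is a special case. It would need a different starting glucose or a different operator decision.
- **The endpoint has no formula.** The infusion rate comes from the power table and the clamp description. Tracer sampling continues through the clamp steady state, so disposal could be derived.

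All four stand as limits on size. Step 5 qualifies the second, because the trigger is read at 1 hour. None closes the gap. The infusion rate is the only operational measure the plan names for this outcome, and nothing says how clamps at different glucose levels are to be compared. It is also fair that a bias against the drug would weaken a true effect and not create a false one, on one of several unranked secondary outcomes.

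**Conclusion.** The plan allows clamp glucose to differ between visits and patients, reads the outcome as a raw infusion rate, and neither normalises nor adjusts for achieved glucose. That much is established from the text.

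The size is not established. The documents give no baseline infusion rate, no higher level and no expected number of patients needing it. Under the assumptions shown, the shift in one patient runs from about 0.2 mg/kg/min to an amount comparable with 1.6. Larger values appear only with higher assumed disposal, which fits the trigger less well. A mean shift of 1.6 would need most patients to switch.

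Smaller numbers still matter in a trial of this size. Two switched patients with a shift of 0.8 each would lower between-group power from 0.46 to 0.30. The likely direction is against the drug. That is argued from the trigger and not shown by data.

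**What to change.** Before any unblinded clamp data are examined, add the following to the analysis plan.

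- Define total body insulin sensitivity as tracer-derived glucose disposal at clamp steady state divided by the achieved steady-state glucose (clearance).
- Report achieved clamp glucose for each patient and visit, by arm.
- Keep the raw infusion rate as a supportive measure.
- Add a sensitivity analysis limited to patients clamped at similar glucose at both visits, with the tolerance fixed in advance. It selects on a post-randomisation feature, so it should stay a sensitivity analysis.

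Dividing the infusion rate by glucose is not an adequate substitute when glucose production is incompletely suppressed. With E = 1 and a plateau of 150 mg/dL, clearance is 1/1.5 = 0.67 mL/kg/min. At 200 mg/dL the infusion rate is 0.67 × 2.0 − 1 = 0.33 mg/kg/min, and 0.33/2.0 = 0.17, a quarter of the true value.

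No new samples are needed. Bedside glucose is taken every 5 minutes during the clamp, and tracer enrichment is already sampled at steady state. The cost is some added analysis. The 0.96 does not transfer directly, because the documents give no SD for the normalised index. Clearance removes the glucose dependence fully only if disposal is proportional to glucose, which is a further reason for the sensitivity analysis. The clamp procedure is left as it is, and no clamp target is proposed.
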